1 PROTOCOL SUMMARY

1.1 SYNOPSIS

Title: Effects of Exercise on Glymphatic Functioning and Neurobehavioral

Correlates in Parkinson's Disease

Study Description: This study will assess patients with a clinical diagnosis of Parkinson's

disease (PD) over prior and following participation in a 12-week community-based exercise program, assessing neuroimaging (beta-amyloid deposition, glymphatic flow), and clinical severity (motor,

cognitive, sleep disturbance, mood).

Objectives: Primary Objective:

Evaluate the glymphatic functioning and beta-amyloid burden response to

12 weeks of a community-based exercise course in PD patients.

Secondary Objectives:

Quantify the association between glymphatic functioning, beta-amyloid

burden, and neurobehavioral dysfunction in PD.

Evaluate the degree to which neuroimaging-based response to exercise

mediates clinical improvement in PD.

Tertiary Objectives:

Evaluate whether the association between glymphatic functioning, betaamyloid burden, and neurobehavioral dysfunction in PD differs between

cognitively healthy and cognitively impaired PD phenotypes.

Evaluate whether the neuroimaging and clinical response to exercise differs between cognitively healthy and cognitively impaired PD

phenotypes.

Quaternary Objectives:

Develop a normative reference group for the Brief Estimate of Seconds Test (BEST) to facilitate PD score interpretation and establish how PD-related neurodegeneration affects time perception. In addition, determine how BEST scores correlate with disease severity, neuroanatomical ROIs, and neuropsychometric cognitive data collected in the previous objectives.

Endpoints: Primary Endpoints:

Glymphatic flow (DTI-ALPS score)
PET/CT (cortical:cerebellar SUVr ratio)

Secondary Endpoints (also used for Tertiary Endpoints):
Unified Parkinson's Disease Rating Scale III (UPDRS-3)

Actigraphy Mini-BEST-est

Freezing Gait Questionnaire

6-minute Walk Tesdt

Hopkins Verbal Learning Test-Revised (HVLT)

Trail Making Test – A & B (TMT)

Stroop Test (Stroop)

Letter Fluency (FAS) Simon Task (Simon)

PROMIS – Sleep Disturbance short forms (PROMIS-Sleep)

Hospital Anxiety and Depression Scale (HADS)

Tertiary Endpoints:

Clinical Dementia Rating Scale (CDR) Brief Estimate of Seconds Test (BEST)

Quaternary Endpoints:

Brief Estimate of Seconds Test (BEST)

Study Population: PD cohort: Patients with a clinical diagnosis of Parkinson's, as defined by

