Spin labeling for cervical LN perfusion. Spin labeling will be performed with an 11-ms hypersecant inversion (labeling) prepulse, followed by an inversion time range of 300 to 2400 ms in 300 ms increments, which will enable blood transit time and perfusion quantification. Other parameters: labeling=STAR; TE=11 ms; spatial resolution=2x2x2 mm3; averages=14.

A.1.2. Analysis and statistical plan.

A.1.2.1 Clinical and neuropsychological examination. MCI will be defined based on established clinical criterion of cognitive performance below 1.5 standard deviations compared to age-based normative expectations in the memory domain and/or the executive functioning domain, with a Clinical Dementia Rating (CDR) of 0 or 0.5, indicating cognitive dysfunction has not contributed to functional dependence for activities of daily living61, 62. The memory domain by determining the mean memory score across performance on the HVLT-R (i.e., Learning Trials 1- 3, Delayed Recall, Delayed Recognition). Similarly, an executive functioning domain will be determined by the mean score across the TMT (part B), Stroop, and Letter Fluency. Clinical analyses will be overseen by Drs. [name] and [name].

A.1.2.2. Image analysis. Analysis will be overseen by the PI and radiology Co-Is Drs. [name] and [name], who together have experience with all image types. Lymphatic spin labeling. Sequential images are acquired (A) without and (B) with magnetic labeling (adiabatic inversion of arterial water spins). Following labeling, blood water flows into LNs (C,D) and attenuates signal. The difference image is proportional to perfusion

(ml/100g/min), which can be quantified upon application of the flow modified Bloch equation (E: T2-weighted image of LNs; F: corresponding perfusion weighted signal). (G) The blood arrival (red) and lymph arrival (black) following labeling over six subjects and LNs (dimensions shown above). The blood signal peaks and decays first, with the magnitude indicating perfusion. The lymph signal peaks later, due to slower lymphatic flow; note that the lymphatic signal is detectable at such long delays due to the longer T1 of lymph (T1=3100 ms) relative to blood (T1=1650 ms).

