SWI analysis. Phase and magnitude data will be combined and a minimum intensity projection calculated. Images will be registered to DTI scans and used for region-of-interest selection.

DTI analysis. Data will be processed using FSL66, including motion- and eddy current-correction, and will be brain-extracted. Tensor eigenvalues and eigenvectors, as well as diffusivity (D) values will be calculated from the diffusion images, b-values, and b-vectors using dtifit. Radiology Co-I [name] will draw regions-of-interest where the lateral projections of the medullary veins (from SWI) are orthogonal to the projection and association fibers, which occurs at approximately the location of the lateral ventricles. Within these regions the diffusivity in x, y, and z (Dxx, Dyy, Dzz) and DTIALPS

score=mean(Dxx,proj,Dxx,assoc)/mean(Dyy,proj,Dzz,assoc) will be quantified67; the primary variable of interest will be bilateral DTI-ALPS score.

Spin labeling analysis. We will follow our previously reported procedures68 and utilize recentlyquantified 3T T1 and T2 LN values. Images will be corrected for motion, pair-wise subtracted, and the flow-modified Bloch equation will be applied to quantify perfusion in absolute units (ml/100g/min). Spin labeling images will be registered to the anatomical image, which will allow us to localize LNs. The primary outcome variable will be mean LN perfusion in cervical LNs.

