Exploratory Hypothesis (2A). Exercise treatment will result in improved glymphatic functioning. Exploratory Hypothesis (2B). Exercise treatment will result in a reduction of cortical beta-amyloid uptake. Exploratory Hypothesis (2C). The degree of improvements in glymphatic functioning and cortical beta-amyloid uptake in response to exercise therapy will be more significant in MCI versus non-MCI participants. D.2.1 Experiment. We will enroll the patients from Aim (1) (A.1.) all of whom are undergoing community-based exercise intervention to treat symptoms of Parkinson's.

A.2.1.1. Exercise intervention procedure. Following baseline assessment, all patients will participate in a community-based kick boxing group exercise class designed for those living with Parkinson's called "Rock Steady Boxing." Patients will complete 12 consecutive, 90-minute, once-weekly classes, then undergo follow-up assessment. Treatment compliance will be monitored by the collaborating exercise trainer. All participants, regardless of degree of treatment compliance will receive follow-up assessment. *A.2.1.2. Imaging procedure.* PET and MRI methods as outlined in A.1.1.2. and A.1.1.3. will be performed.

A.2.2. Analysis and statistical plan. Our main hypotheses are that after 12 weeks of once-weekly exercise treatment for PD, glymphatic functioning (per DTI-ALPS) will improve and beta-amyloid burden (per PET) will decline. We expect that degree of treatment compliance standards will moderate these changes. We will also explore whether scalar degree of treatment compliance relates to degree of change in our assessment modalities. Statistical analysis will be overseen by statistics Co-I [name] and the same considerations outlined in Aims (1) will be applied. To test Exploratory Hypothesis (2A), a paired Student's t-test or Wilcoxon signed-rank test, depending on normality findings, will be applied to determine if glymphatic flow (DTI-ALPS score) is increased after, relative to before, exercise intervention. To test Exploratory Hypothesis (2B), an identical

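### No reader masking, reading order or cross-visit region rule is specified for the hand-drawn DTI-ALPS score, one of two primary endpoints, tested pre-post without a control group

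*SAP*

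**What the plan says.** The Protocol synopsis (1.1) lists two primary endpoints, the DTI-ALPS score and the cortical:cerebellar SUVr. Its primary objective is the response of glymphatic functioning and beta-amyloid burden to 12 weeks of exercise.

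SAP A.1.2.2 (DTI analysis) says that a radiology co-investigator "will draw regions-of-interest where the lateral projections of the medullary veins (from SWI) are orthogonal to the projection and association fibers". It gives the site only loosely, as roughly level with the lateral ventricles. The score is a ratio of diffusivities within those regions, and "the primary variable of interest will be bilateral DTI-ALPS score". On responsibility for image reading, the same section says "Analysis will be overseen by the PI and radiology Co-Is".

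For Hypothesis 2A, SAP A.2.2 says that "a paired Student's t-test or Wilcoxon signed-rank test, depending on normality findings, will be applied to determine if glymphatic flow (DTI-ALPS score) is increased" following exercise. There is no comparison group: the Aim 2 participants are the Aim 1 patients, "all of whom are undergoing community-based exercise intervention to treat symptoms of Parkinson's". The SAP labels 2A exploratory, yet A.2.2 also counts the pre-post improvement among its main hypotheses.

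The same score is used in Hypothesis 1A (correlation with SUVr) and Exploratory Hypothesis 1B (MCI versus non-MCI), both in A.1.3.

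Neither document mentions masking of the reader, reading order, a second reader, or whether regions are redrawn or carried over at follow-up. A.2.1.2 says only that the PET and MRI methods are repeated.

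**The concern.** Where the regions are placed determines the score, and the location rule is approximate, so the reader has some discretion. A reader who knows which scan follows exercise, and who expects improvement, may place regions slightly differently at the two visits without intending to. In a randomised comparison with masked arms, a shift of that kind would fall on both arms and largely cancel. Here everyone exercises, so a shift between visits is added in full to the estimated mean change.

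Two other uses of the score are open to different mechanisms. Knowledge of MCI status could move the 1B contrast, and knowledge of a participant's SUVr could move the 1A correlation, which is the only one of these three hypotheses that the SAP does not label exploratory.

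A separate issue is precision. If regions are redrawn independently at each visit, placement error enters every change score twice.

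**Working it through.** **Inputs.** Sample size: 32 PD participants, 16 per MCI group (SAP A.1.1), or 50, 25 per group (Protocol 2.1). Test: two-sided 5%, paired t-test (SAP A.2.2). Attrition: 10% (SAP section B). Reader shift: not in the documents. Values of 0.1, 0.2 and 0.3 SD of within-person change are assumed.

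**The plan's own figures.** The only fully specified power figure for DTI-ALPS is 82% for a correlation of -0.49 at n=32 (A.1.3). With Fisher's z, power = Φ(atanh(0.49)·√(32−3) − 1.960) = Φ(0.536 × 5.385 − 1.960) = Φ(0.927) = 82.3%, so it reproduces. The claim of at least 80% power for the pre-post test (A.2.2) cannot be checked, because no DTI-ALPS effect or SD of change is given. At n=32, 80% power corresponds to a standardised mean change of 0.51; at n=50, to 0.40.

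**Hypothesis 2A with a reader shift and no true change.** If the reader adds a mean shift of d SD to the change score, the paired t statistic follows a noncentral t with n−1 degrees of freedom and noncentrality d·√n. The rejection rate is P(|T| > t(0.975, n−1)).

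| Assumed shift d | d·√32 | Rejection, n=32 | d·√50 | Rejection, n=50 |
|---|---|---|---|---|
| 0 | 0 | 5.0% | 0 | 5.0% |
| 0.1 | 0.57 | 8.5% | 0.71 | 10.7% |
| 0.2 | 1.13 | 19.5% | 1.41 | 28.4% |
| 0.3 | 1.70 | 37.6% | 2.12 | 54.8% |

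For a shift towards improvement, nearly all of these rejections are in the hypothesised direction: 7.9%, 19.4% and 37.6% at n=32. After 10% attrition (0.9 × 32 ≈ 29; 0.9 × 50 = 45), the 0.2 SD row becomes 18.0% and 25.9%. A larger sample makes a fixed bias more likely to reach significance, so the Protocol's n=50 gives no protection.

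**Hypothesis 1B.** Here the relevant quantity is a differential shift between MCI groups, in units of the within-group SD of the score. Noncentrality is d·√(m/2) with m per group. At d=0.2 and m=16 it is 0.2 × √8 = 0.57, and rejection is 8.5%. At m=25 it is 0.2 × √12.5 = 0.71, and rejection is 10.7%. At d=0.3 the rates are 13.0% and 18.0%. For the same d these are well below the 2A figures.

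**Independent redrawing.** If placement error has variance σ² at each visit and is not directional, the variance of the change score rises by 2σ² and its mean is unchanged. That costs power and does not raise the false-positive rate. The documents give no σ, so the loss cannot be sized.

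**The case against.** The strongest case on the other side has five parts.

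First, the documents are silent; they do not say that the reader is unmasked or that regions are redrawn at each visit. A reader might infer open reading, but the text does not support it. The accurate statement is that no masking is specified.

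Second, the SAP labels 1B and 2A exploratory. This lowers the stakes within the SAP. However, the Protocol makes the exercise response its primary objective and DTI-ALPS a primary endpoint, so the point remains material.

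Third, discretion is limited. Regions follow veins seen on SWI, the score is a fixed formula, and a directional bias requires placements that tend to raise the ratio. SAP section D also says that the methods, glymphatic flow included, have been evaluated for reproducibility. These points narrow the risk. They do not remove it: no reader-agreement figure is given for DTI-ALPS (the only one, ICC=0.81, is for CSF flow velocity), and a reader can be consistent and still be shifted by expectation.

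Fourth, any assumed bias inflates a t-test, so the table shows how sensitive the design is and not how this reader behaves. That stands in full. One might infer that a positive 2A result would be the reader's doing; nothing in the documents shows that.

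Fifth, the other primary endpoint, SUVr, does not rest on these regions, so this is not a defect of the primary imaging outcome as a whole.

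**Conclusion.** The point holds as a cheap improvement that should be made before scans are read. The plan can be followed exactly with open reads in visit order, and in a single-group pre-post design nothing downstream would absorb a reader shift. If that shift were 0.1 to 0.3 SD of change and exercise had no effect, the nominal 5% test would reject 8.5% to 37.6% of the time at n=32, and 10.7% to 54.8% at n=50. The arithmetic is firm; the shift sizes are assumptions, and the documents offer no figure to narrow them.

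Three stronger readings should be avoided. The documents do not establish that reading is unmasked. 1B is not exposed in the same way or to the same degree as 2A (8.5% against 19.5% at 0.2 SD with 32 participants in total). Redrawing regions is a matter of lost power, not of false positives. The possible effect of SUVr knowledge on 1A is real in principle but has not been quantified.

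**What to change.** Add to SAP A.1.2.2, under DTI analysis, one of two rules:

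1. DTI and SWI sets are coded, with identifiers, visit, date, MCI status and PET result removed, and are read in random order by the same reader, either after follow-up is complete or in batches that mix visits.
2. Regions are drawn once per participant on a masked visit, with MCI status and PET result withheld, and carried to the other visit by registration, so that both scores come from the same region.

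Rule 2 also removes the noise from independent redrawing, but the registration needs a masked quality check. Under either rule, repeat-read agreement on a subset would supply the missing reader-variance figure.

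The cost is a coding list and a random order, held by someone other than the reader, and some delay to reads. No extra scans or participants are needed. The delay matters in one place: SAP section B lets Aim 1 findings influence which measures are used in Aims 2 and 3. Mixed batches, or masked baseline reads with regions carried forward, limit that delay. A.1.2.2 also has a radiology co-investigator review the MRIs for infarcts and grade the angiography. Names are removed, so it is unclear whether this is the same person. If it is, that review should be kept apart from the coded reads.

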1 STATISTICAL PLAN

1.1 AIM 1

Aim (1). To quantify the relationship between CNS lymphatic measures and beta-amyloid burden.

- Hypothesis (1A). Glymphatic flow and lymphatic collector velocity inversely correlate with beta amyloid measured from 18F-florbetapir PET in older adults with Parkinson's disease.
- Exploratory Hypothesis (1B). In Parkinson's subjects matched for age and sex, glymphatic flow and betaamyloid burden will be worse in patients with versus without mild cognitive impairment (MCI).

A.1.1 Experiment. We will enroll participants with idiopathic Parkinson's disease (n=32; age range=55- 80 years), equally distributed and matched for age and sex between groups with (n=16) and without (n=16) mild cognitive impairment. These populations provide a cohort to evaluate the potential relationship between glymphatic flow and beta-amyloid burden, given the elevated risk of beta-amyloid accumulation associated with both conditions. These patients will form a cohort to be assessed before and after a community-based exercise intervention. Participants will be recruited from Vanderbilt University Medical Center Neurology's Behavioral and Cognitive and Movement Disorder Clinics by Drs. [name] and [name]. Potential participants will undergo a neurological and neuropsychological examination to characterize their medical and neurobehavioral status. Patients will have medical and motor presentation indicated for the community-based exercise program. Those patients with clinically-defined MCI, will be without evidence of vascular cognitive impairment, primary mood disorder, Lewy body disease, or comorbid medical condition that could contribute to cognitive symptoms (e.g. pulmonary, hematologic, metabolic, or vitamin deficiency).

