A.1.3. Statistical concerns. Statistical analyses will be overseen by statistician Co-I [name]. Descriptive statistics, including means, standard deviations, and ranges for continuous parameters, as well as percent and frequency for categorical parameters, will be presented. Tests for normality and homoscedasticity will be made. To test Hypothesis (1A), Pearson or Spearman (depending on normality findings) will be applied to evaluate the relationship between glymphatic flow, measured as the DTIALPS score, and the cortical:cerebellar SUVr, measured from PET. As an exploratory analysis to understand whether the relationship is spatially dependent, correlation testing will be repeated using the regional SUVr measures and corrected p-values reported. Power calculations are based on preliminary data in six MCI subjects in which an inverse correlation (Spearman's alpha =-0.49) was found between SUVr and DTI-ALPS score. With a sample size of 32, we should have 82% power to detect a correlation of -0.49 with two-sided p<0.05. To test Exploratory Hypothesis (1B), we will apply a Student's t-test or Wilcoxon rank-sum test (depending on normality findings), to evaluate whether mean glymphatic flow, measured as the DTI-ALPS score, is different between age- and sex-matched participants with vs. without MCI. Motivation is based on our preliminary data, where we have observed a large effect size (Cohen's d=2.3) in DTI-ALPS score between age- and sex-matched subjects with vs. without MCI.

A.1.4. Impact. Results will for the first time evaluate how the proposed human CNS lymphatic system and levels of beta-amyloid burden are altered in Parkinson's disease. If confirmed, results will motivate the use of evaluating human CNS lymphatic dysfunction with proposed methods for understanding betaamyloid clearance disorders.

A.2. Aims (2). Quantify the glymphatic functioning and beta-amyloid burden response to 12 weeks of a community-based exercise course developed specifically for PD patients.

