Patient heterogeneity is a concern. Since other clinical factors can affect brain and cognitive functioning, we plan to control for age and screen for the most common medical conditions that might disproportionally affect outcome assessments. Furthermore, we have selected an age-cutoff that reduces clinical heterogeneity and has extant support for the presence of our conditions-of-interest. Patient recruitment. Vanderbilt University Medical Center's Neurology division has a large clinical volume of adult patients with Parkinson's. Thus, our recruitment target is felt to be reasonable. Patient attrition. We have accounted for a possible 10% attrition/exclusion in our protocol. We will use compliance as a scalar variable, allowing us to retain all patients at follow up, regardless of degree of compliance.

C. Sex as a biological variable. Given the relative infancy of the field of human CNS lymphatic imaging, to our knowledge there is no literature reporting sex differences for all proposed biomarkers of the lymphatic drainage system. Therefore, we have powered our study to specifically address this concern, and subjects will be recruited equally for both sexes and statistical measures are in place to evaluate how each observable varies with biological sex. This should be the first study to report how these properties of the lymphatic system differ with biological sex in humans.

D. Scientific rigor and reproducibility. The need to understand CNS small blood and lymphatic vessels is becoming increasingly recognized, with more than 150 manuscripts published in the last five years on this topic. However, nearly all studies utilize animal models only, and there is much less information available on how this system operates in humans in health or in the presence of clearance disorders such as Alzheimer's disease. One reason for this is that reliable methods for evaluating lymphatics in vivo are underdeveloped. Methods proposed here (e.g., CVR compliance, lymphangiography, glymphatic flow, and CSF flow velocity)

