have already been evaluated by us for reproducibility, and lymphatic methods have been optimized in prior work in patients with lymphatic insufficiency of known etiology (e.g., A.1.3.). Finally, each aim includes a statistical analysis section in which power calculations are provided based on our preliminary data and available extant literature. The statistical analysis of all aims will be overseen by biostatistician collaborator [name] to ensure responsible analysis and interpretation of the results.

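### SAP section C says the study is powered for sex differences, but no listed test or power figure involves sex; a smaller gap is that section B promises age control that the Hypothesis 1A correlation does not contain

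*SAP*

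**What the plan says.** **Sex.** SAP section C notes that the literature on sex differences in these biomarkers is lacking, and continues: "Therefore, we have powered our study to specifically address this concern, and subjects will be recruited equally for both sexes". It adds that "statistical measures are in place to evaluate how each observable varies with biological sex", and expects that "This should be the first study to report how these properties of the lymphatic system differ with biological sex in humans". Section D states that "each aim includes a statistical analysis section in which power calculations are provided based on our preliminary data and available extant literature".

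**Age.** SAP section B, under patient heterogeneity, says "we plan to control for age and screen for the most common medical conditions", and presents the age cutoff as a further measure. It names no method of age control.

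**The 1A test.** Aim 1 states Hypothesis 1A as: "Glymphatic flow and lymphatic collector velocity inversely correlate with beta amyloid measured from 18F-florbetapir PET in older adults" with Parkinson's disease. A.1.3 describes the test as follows: "Pearson or Spearman (depending on normality findings) will be applied to evaluate the relationship between glymphatic flow, measured as the DTIALPS score". The other variable is SUVr from PET. The power statement is that, with 32 participants, "we should have 82% power to detect a correlation of -0.49 with two-sided p<0.05".

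**Where age and sex do enter.** They enter by design only: matching of the MCI and non-MCI groups on both (A.1.1, A.1.3), the 55-80 age range (A.1.1, section B), age-based norms in the MCI definition (A.1.2.1), and equal recruitment of the sexes (section C).

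**The concern.** Sections B and C describe analyses and power that the analysis sections do not contain.

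For sex, the SAP claims power without naming a comparison, a target difference or a power value, while expecting to be first to report such differences. If a sex comparison is then run and is not significant, a reader of section C could take it as adequately powered evidence of no difference.

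For age, DTI-ALPS and amyloid burden might both change with age. If they do, some of an inverse correlation across participants aged 55 to 80 could reflect shared ageing. A reader who relies on section B would suppose that this had been dealt with. The result at stake is the association between glymphatic function and amyloid burden, which is part of a secondary objective in the Protocol synopsis.

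**Working it through.** **1. Is there a sex or age term anywhere?**

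| SAP section | Analysis | Age or sex term | Basis of power |
|---|---|---|---|
| A.1.3, 1A | Pearson or Spearman correlation of DTI-ALPS with SUVr | none | r=-0.49, n=32, 82% |
| A.1.3, 1B | t-test or rank-sum test, MCI v non-MCI | matching only | none computed; preliminary d=2.3 cited as motivation |
| A.2.2, 2A-2C | Paired tests, repeated within MCI subgroups; regression on compliance and amyloid change | none | pre/post, at least 80% |
| A.3.2, 3A-3D | Paired tests; regressions with cognitive or PROMIS scores | none | published effect sizes for cognition |

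No row estimates a sex effect, and no power figure uses sex.

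**2. The plan's own 1A figure.** Inputs from A.1.3: n=32, r=-0.49, two-sided 5%. By Fisher's z, power = Φ(atanh(0.49) × √(n−3) − 1.96) = Φ(0.536 × 5.385 − 1.96) = Φ(0.927) = 82.3%. The stated 82% therefore reproduces as a two-variable correlation with no covariate.

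**3. What the cohort offers for sex.** Assume equal numbers by sex, as section C intends: 16 v 16 (SAP n=32) or 25 v 25 (Protocol section 2.1, n=50). Power comes from the two-sample noncentral t distribution with 2m−2 degrees of freedom and noncentrality d√(m/2), where m is the number per sex. The 95% CI half-width in SD units is t(0.975, 2m−2) × √(2/m). The documents give no sex effect, so the values of d are assumed.

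| | 16 v 16 | 25 v 25 |
|---|---|---|
| d for 80% power | 1.02 | 0.81 |
| Power at d=0.3 | 13% | 18% |
| Power at d=0.5 | 28% | 41% |
| Power at d=0.8 | 59% | 79% |
| CI half-width | 2.042 × 0.354 = 0.72 | 2.011 × 0.283 = 0.57 |

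**4. How much age could matter for 1A.** The documents give no age correlations, so a range is assumed. Suppose that age is the only link and correlates −a with one measure and +a with the other. The induced correlation is then −a². With age uniform and 100,000 simulated trials per scenario, the unadjusted test is significant as follows:

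| a | Induced r | n=32 | n=50 |
|---|---|---|---|
| 0.2 | −0.04 | 5.6% | 5.8% |
| 0.3 | −0.09 | 7.6% | 9.4% |
| 0.4 | −0.16 | 14% | 20% |
| 0.5 | −0.25 | 28% | 42% |

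The age-partial test stays at about 5% throughout. The excess is small for a of 0.3 or less.

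**5. What adjustment would do to power if it replaced the planned test.** With k covariates, n−3 becomes n−3−k. If the partial correlation stays at −0.49, an age term gives 81.0% at n=32 and 95.3% at n=50. If −0.49 is instead the unadjusted value, the partial correlation is (−0.49 + a²)/(1 − a²):

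| a | Partial r | Power, n=32 | Power, n=50 |
|---|---|---|---|
| 0.2 | −0.47 | 77% | 93% |
| 0.3 | −0.44 | 70% | 89% |
| 0.4 | −0.39 | 59% | 80% |
| 0.5 | −0.32 | 42% | 61% |

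For a partial rank correlation, with variance 1.06/(n−3−k), power at n=32 is about 78.7% even if the partial value stays at −0.49.

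**The case against.** On sex, the best defence is that equal recruitment and matching already take sex into account. Balance does help a sex comparison, but it neither specifies nor powers one. The claim could hold only for large differences, and the SAP names none.

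On age, the defence is stronger. The sentence in section B is ambiguous. It names no covariate, it stands beside medical screening, and the SAP has real design controls: matching, the age limit and age-based norms. These serve 1B. They do not reach 1A, because two groups with the same age distribution still contain the full age spread when pooled.

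Two stronger readings are tempting, and the documents do not support them.

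- *The 1A test is invalid or has an inflated error rate.* Aim 1 states a marginal inverse correlation, and A.1.3 tests exactly that. The rates in step 4 describe detection of a real, age-driven association; they are not type I error for that hypothesis. The larger ones need age correlations of 0.4 to 0.5 and no other link, neither of which the documents establish.
- *The 1A test should be replaced by an age-adjusted one.* That would change the quantity estimated and could cost much power at n=32 (step 5). Nor would it settle the interpretation. A.1.3 cites preliminary d=2.3 in DTI-ALPS by MCI status, which with equal groups is a correlation of 2.3/√(2.3² + 4) = 0.75, and 1B expects amyloid to differ by MCI status too. MCI status is thus another possible shared source that age adjustment alone would leave in place.

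**Conclusion.** The sex statement is wrong as written. The SAP claims power and statistical measures for sex but contains neither. At its own sample size, with equal numbers by sex, only a difference of about one SD (d=1.02) would be found with 80% power; at the Protocol's n=50 the figure is 0.81.

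The age point is real but secondary. Section B promises control that 1A does not show, so a significant 1A result could not be separated from shared ageing. How much this matters depends on age correlations that the documents do not give, and it is slight if they are 0.3 or less.

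Overall this is minor. The 82% for 1A stands. Hypothesis 1B is protected by matching, and the pre/post primary objective rests on within-person comparisons that need no such adjustment.

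**What to change.** - **Section C.** Replace the statement that the study is powered for sex with an exploratory comparison by sex, reported as an estimate with 95% CI. State the detectable difference at 80% power for equal numbers: d about 1.02 at 16 v 16, or 0.81 at 25 v 25, according to the sample size that applies.
- **A.1.3.** Keep the planned unadjusted Pearson or Spearman correlation as the 1A test, with its stated 82% power. Add an age-adjusted partial (or partial rank) correlation as a supporting sensitivity analysis, with no power claim. Say that it addresses age only and that MCI status is another possible shared source.
- **Section B.** Say how age is controlled: by matching for 1B, by the age limit, and by this sensitivity analysis for 1A.

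The cost is SAP wording and a little extra analysis. No new data are needed, since the Protocol's Schedule of Activities collects demographics at screening. The adjusted estimate may be weaker and less precise than the planned one, which is a reason to fix its supporting role in advance.
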